Investigational Product(s):	rVA576 (Coversin) powder for solution for subcutaneous injection, 18mg/vial	
Phase of Development:	III	Indication: Long term management of patients with diseases including PNH and aHUS
Study Center(s):	Multi-centre	
Objectives:	Primary Objective: To determine the safety profile of long-term rVA576 (Coversin) treatment.	
Study Design:	Open-label, non-comparative	
Planned Number of Subjects:	Approximately 50 patients	
Subject Population:	Patients with diseases requiring complement inhibition who have previously taken part in Akari clinical trials and who wish to continue to receive rVA576 (Coversin) after their active participation in the previous trial has completed and patients treated under compassionate use or named patient arrangements who wish to continue on rVA576 (Coversin) therapy.	
Criteria for Inclusion:	Inclusion Criteria: 
 1) Patients 18 years and above treated with rVA576 (Coversin) under other Akari clinical trial protocols and wish to remain on rVA576 (Coversin) at the conclusion of that trial. 2) In the opinion of the treating responsible clinician patient is receiving clinical benefit from continued treatment with study drug. 3) Evidence of sustained complement inhibition by CH50 assay. 4) Women of childbearing potential (WOCBP) must agree to use effective contraception consistently throughout the study and have a negative pregnancy test at screening. Women are considered post-menopausal and not of childbearing potential if they have had 12 months of amenorrhea and considered sterile if they have had surgical bilateral oophorectomy (with or without hysterectomy) or tubal ligation at least six weeks previously. 5) Males with a childbearing potential partner must agree to use effective contraception consistently OR have had a vasectomy. 6) Weight \geq50kg. 	

	
7) Received appropriate prophylaxis against Neisseria meningitidis infection, by both immunisation and continuous or intermittent antibiotics.
 
8) Patient is willing to give voluntary written informed consent.
 
9) The patient is willing in the process of preparation and self-administration of the study drug.

Criteria for Exclusion:	
Exclusion Criteria:
 
 1. Patient experienced any safety event in the previous study protocol, which puts the patient at unacceptable risk in the current protocol in the clinical judgement of the investigator and sponsor. 2. Patient is unwilling to complete the Quality of Life instruments and diary cards. 3. Active meningococcal infection (section 4.3.2 for additional information). 4. Any other reason for which, in the opinion of the Investigator, it would not be in the interests of the patient to remain on rVA576 (Coversin). 5. If female, the subject is pregnant or lactating or intending to become pregnant before, during, or within 90 days after last dose; or intending to donate ova during such period. 6. If male, the subject intends to donate sperm during this study or for 90 days after last dose. 7. Failure to satisfy the Investigator of fitness to participate for any other reason or any condition which, in the opinion of the investigator, could increase the subject's risk from participating in the study or confound the outcome of the study. 8. Use of prohibited medication (e.g. Eculizumab (Soliris®), Chemotherapeutic agents, any other drug acting directly on the complement system). 9. The subject has a history of drug abuse (defined as any illicit drug use) or a history of alcohol abuse within one year prior to screening. 10. Participation in other clinical trials with investigational product.
Concurrent control	None
Treatment Regimen:	
Test Product, Dose and Mode of Administration:
 
rVA576 (Coversin) 18 mg/vial powder for solution for injection. When the contents of one vial are reconstituted with 0.6 mL Water for Injection (WFI) and drawn up according to the instruction manual the resulting solution consists of rVA576 (Coversin) 30mg/mL in an extractable volume of greater than or equal to 0.5mL phosphate-buffered saline (PBS), pH 7.2. The product is administered subcutaneously.
 
It is expected that all patients being treated under this protocol will have been on a stable dose of rVA576 (Coversin) prior to entering the study and will remain on that dose initially. Should a change in dose or dose

frequency become desirable, the responsible investigator will have discretion to alter the treatment regime in consultation with the Sponsor's medical representative. During any such changes careful monitoring of complement inhibition is mandatory and this should include regular assessment of haematological/biochemical parameters (e.g. serum LDH) and CH50 as well as the patient's clinical status.

In the event of an increase of dose or dose frequency, an ablating dose (AD) may be given to ensure complete complement inhibition before the new dose is started. It is assumed that a reduction of dose or dose frequency would only be considered if the patient's prior complement control was adequate and so no AD need be given before commencing the new dose.

The ablating dose (AD) consists of 2 doses; an initial dose of 60mg followed 12 hours later by 1 dose of 30mg. A suggested regimen to be followed in the event of an inadequate response to rVA576 (Coversin) treatment is given below:

PNH patients

Ablating Doses (if required)			
Dose		Interval	
60mg		Single dose	
30mg		1 x 12 hourly dose	
Inadequate Response			
Existing		Switch to	
Dose	Interval	Dose	Interval
15mg	12 hourly	22.5mg	12 hourly
22.5mg	12 hourly	45mg	24 hourly
30mg	24 hourly	45mg	24 hourly
45mg	24 hourly	22.5mg	12 hourly

aHUS patients

Ablating Doses (if required)	
Dose	Interval
60mg	Single dose
30mg	1 x 12 hourly dose
Inadequate Response	

	Existing		Switch to	
	Dose	Interval	Dose	Interval
	30mg	12 hourly	After assessment decision will be made in collaboration with the Sponsor and PI.	
	45mg	24 hourly	30mg	12 hourly
Duration of Treatment:	
Up to 4 years
 
Patients for whom rVA576 (Coversin) was found to be effective in this clinical trial and who wish to continue on the drug following conclusion of this trial, will continue to receive rVA576 (Coversin), subject to approval of the applicable governmental agency, until rVA576 (Coversin) receives marketing approval or another treatment of benefit becomes available. If Akari encounters any issues with the availability of the drug, it will allocate available drug to such patients in a manner which is fair and consistent with ethical requirements.
			

1. Introduction

rVA576 (Coversin) is a small protein complement C5 inhibitor which prevents the cleavage of C5 by C5 convertase into C5a and C5b and thereby inhibits generation of the membrane attack complex, C5b-9 (MAC). It is effective in inhibiting terminal complement activity irrespective of the activating pathway. [REDACTED]

[REDACTED]

[REDACTED]

[REDACTED]

[REDACTED]

[REDACTED]

[REDACTED]

[REDACTED]

[REDACTED]

1.1. PNH

PNH is an acquired genetic haemolytic anaemia, in which failure to synthesise GPI-anchored proteins prevents affected blood cells from attaching the complement regulatory proteins CD55 and CD59 to their surface, making them vulnerable to attack by normal background complement activity. The resulting intravascular haemolysis of affected red blood cells (RBC) causes free haemoglobin to be released into the bloodstream. Some lysis of RBC may also be extravascular caused by complement deposition on cell surfaces and subsequent phagocytosis via the reticulo-endothelial system, in particular Kupfer cells and splenic phagocytes [Brodsky et al, 2014]. In the bloodstream, free haemoglobin causes depletion of nitric oxide with resultant smooth muscle spasm causing or contributing to symptoms such as dysphagia, erectile dysfunction, abdominal pain and, possibly, pulmonary hypertension.

PNH is characterised by red blood cell haemolysis, large vessel thrombosis particularly affecting the hepatic, visceral, cerebral and dermal veins and impaired haematopoiesis. The relationship between aplastic anaemia and PNH is not fully understood, however there is a greater incidence of PNH in patients with a history of aplastic anaemia, possibly because PNH clones have a higher rate of proliferation in this condition than normal stem cells. Treatment of aplastic anaemia with immunosuppressants is known to increase PNH clone size but whether the cells so produced are more or less susceptible to haemolysis than other PNH cells remains controversial. PNH patients with bone marrow aplasia are more likely to require blood transfusion because of the impaired production of normal red cells.

Treatment of PNH is by bone marrow allograft or, where available, by terminal complement blockade with the only approved complement C5 inhibitor, the monoclonal antibody eculizumab. Untreated, patients with PNH have a reduced life expectancy, principally because of major thrombotic events. Side effects of repeated blood transfusion, such as iron accumulation, also contribute to the morbidity of the disease.

1.2. aHUS

Atypical HUS is caused by a disorder in complement regulation, which leads to leukocyte and platelet activation, thrombotic microangiopathy, and subsequent end-organ damage [Thomson & Ulrickson, 2016]. Atypical HUS is distinguished from other more common causes of haemolytic uraemic syndrome, the commonest being Shigatoxin-producing *Escherichia coli* (STEC) and *Streptococcus pneumoniae*. The most common causes of atypical HUS are specific complement gene mutations that predispose towards development of the disease, while antibodies to complement factor H have also been implicated in a smaller subset of patients. Classic laboratory findings include haemolytic anaemia, thrombocytopenia, and acute kidney injury. Atypical HUS is distinguished from thrombotic thrombocytopenic purpura (TTP) by its lack of reduction in activity of ADAMTS13 (A disintegrin and metalloproteinase with a thrombospondin type 1 motif, member 13).

Untreated aHUS is associated with permanent renal dysfunction, high recurrence rate, and high mortality. Historically, prognosis was poor: studies showed that 33–40% of patients progressed to end stage renal disease (ESRD) or death during the first clinical manifestation. Plasma therapy in the form of plasma exchange or infusion has remained the standard treatment for aHUS. However, many patients do not respond to plasma therapy and some require prolonged treatment. Within 1 year of diagnosis, up to 65% of patients managed with plasma exchange (PEX) suffered permanent renal damage, progressed to ESRD, or died. The elucidation of the pathogenesis from uncontrolled activation of the alternative complement pathway, resulting in formation of the MAC C5b-9 has ultimately led to approval in EU and in USA for treatment with eculizumab, a monoclonal IgG antibody that binds to C5 and prevents subsequent formation of terminal complement.

Patients being admitted to this study will have previously received treatment with rVA576 (Coversin) under different investigational protocols for PNH, for eculizumab resistance or aHUS.

[REDACTED]

2.1. [REDACTED]

[REDACTED]	[REDACTED]	[REDACTED]	[REDACTED]
[REDACTED]	[REDACTED]	[REDACTED]	[REDACTED]
[REDACTED]	[REDACTED]	[REDACTED]	[REDACTED]
[REDACTED]	[REDACTED]	[REDACTED]	[REDACTED]
[REDACTED]	[REDACTED]	[REDACTED]	[REDACTED]
[REDACTED]	[REDACTED]	[REDACTED]	[REDACTED]
[REDACTED]	[REDACTED]	[REDACTED]	[REDACTED]

Table 1: aHUS Recommended Vial Usage

[REDACTED]	[REDACTED]	[REDACTED]	[REDACTED]
[REDACTED]	[REDACTED]	[REDACTED]	[REDACTED]
[REDACTED]	[REDACTED]	[REDACTED]	[REDACTED]
[REDACTED]	[REDACTED]	[REDACTED]	[REDACTED]

[REDACTED]
[REDACTED]
[REDACTED]

[REDACTED]
[REDACTED]
[REDACTED]
[REDACTED]
[REDACTED]

[REDACTED]
[REDACTED]
[REDACTED]

[REDACTED]
[REDACTED]
[REDACTED]
[REDACTED]

[REDACTED]
[REDACTED]
[REDACTED]
[REDACTED]
[REDACTED]
[REDACTED]

[REDACTED]

[REDACTED]

[REDACTED]

[REDACTED]

[REDACTED]

[REDACTED]

[REDACTED]

[figure not shown]
[REDACTED]

[REDACTED]

[REDACTED]

[REDACTED]

[figure not shown]
[REDACTED]

[Redacted]

[Redacted]

[Redacted]

[REDACTED]

[REDACTED]

[REDACTED]

[REDACTED]

[REDACTED]

[REDACTED]

[Redacted text block]

[Large redacted text block]

[figure not shown]
[Redacted text block]

[Redacted text block]

2.4. [Redacted section header]

[Redacted text block]

[REDACTED]	[REDACTED]	[REDACTED]					
		[REDACTED]	[REDACTED]	[REDACTED]	[REDACTED]	[REDACTED]	[REDACTED]
[REDACTED]		[REDACTED]	[REDACTED]	[REDACTED]	[REDACTED]	[REDACTED]	[REDACTED]
[REDACTED]							
	[REDACTED]						
	[REDACTED]						
	[REDACTED]						
	[REDACTED]						
	[REDACTED]						
	[REDACTED]						
	[REDACTED]						
[REDACTED]							
	[REDACTED]						
	[REDACTED]						
	[REDACTED]						
	[REDACTED]						
[REDACTED]							
	[REDACTED]						
	[REDACTED]						
[REDACTED]							

[Redacted text block consisting of approximately 14 lines of blacked-out content.]

[Redacted text block]

[Large redacted text block]

[Redacted text block]

[Redacted text block]

[REDACTED]

[REDACTED]

[REDACTED]

[REDACTED]

[REDACTED]

[REDACTED]

[REDACTED]

[REDACTED]

3. Trial Purpose, Objectives and Endpoints

3.1. Trial purpose & Objectives

The objective of the trial is to provide a database of information regarding long-term administration of rVA576 (Coversin) to show that it remains safe for long periods and is

[REDACTED]

acceptable to patients and show that the effect observed in the previous clinical trial is maintained. It also provides the opportunity to adjust an individual patient's dose or dose frequency should it be considered desirable. All patients enrolled into the CONSERVE study will have transitioned from a parent clinical trial.

The specific objectives of the study are:

- To observe the long term safety and efficacy of rVA576 (Coversin) in a period exceeding the 6 months of treatment.
- To assess the long term patient acceptability of rVA576 (Coversin) using the EORTC QLQ-C30 (for some PNH only), EQ-5D-5L & FACIT-F (both PNH & aHUS) instruments and the Sponsor non validated questionnaire.
- To observe the changes, if any, in the production of anti-drug antibodies (ADA) and whether such antibodies are, or become, neutralising

3.2. Endpoints

3.2.1. *Safety & Efficacy Endpoints:*

Primary:

- Long term safety of rVA576 (Coversin) therapy as assessed by AEs, serious adverse events (SAEs), vital signs, results of standard laboratory tests (clinical chemistry, haematology and urinalysis), and results of electrocardiograms (ECGs).

PNH Secondary:

1. Proportion of subjects with thrombotic and haemolytic event-free status during each 3 month time period since the start of the study.
2. Time to thrombotic or haemolytic event since the start of the study.
3. Proportion of subjects who require PRBC transfusion during each 3-month period since the start of the study and over the entire period of the study, with analysis of i) subjects who were transfusion-dependent when they started receiving rVA576 (Coversin), ii) subjects who were transfusion-independent when they started receiving rVA576 (Coversin), and iii) all subjects, and further stratification of these proportions by a) patients who were complement inhibitor-naïve prior to treatment with rVA576 (Coversin), and b) patients who received treatment with another complement inhibitor before switching to rVA576 (Coversin).
4. Time to first transfusion since joining the study.
5. Proportion of subjects with no adverse change in overall scores of Quality of Life using the EORTC QLQ-C30, the EQ-5D-5L and FACIT-F instruments at each 3-month time period since the start of the study.
6. Proportion of subjects with serum Lactate Dehydrogenase (LDH) ≤ 1.8 , >1.8 to 2.4, >2.4 to 3, and >3 times the upper limit of normal (ULN) at each 3-month time period since the start of the study.

7. Proportion of subjects with median serum Lactate Dehydrogenase (LDH) ≤ 1.8 , >1.8 to 2.4 , >2.4 to 3 , and >3 times the upper limit of normal (ULN) over the entire duration of the study.
8. Proportion of transfusion-independent subjects at each 3-month time point, with haemoglobin (g/L) above the baseline haemoglobin value they had at the start of the trial from which they entered CONSERVE. With baseline for CAPSTONE (AK580) defined as the haemoglobin value at which they received their qualifying transfusion (the set point) or for COBALT (AK579) and CONSENT (AK578) the haemoglobin value at which patients entered those trials. With separate analysis of subjects who were i) transfusion-independent prior to receiving rVA576 (Coversin) and remain transfusion-independent and ii) transfusion-dependent prior to receiving rVA576 (Coversin).
9. Proportion of transfusion-independent subjects over the entire duration of the study with mean haemoglobin (g/L) above the baseline haemoglobin value they had at the start of the trial from which they entered CONSERVE. With baseline haemoglobin defined as for the previous secondary endpoint (#8). With separate analysis of subjects who were i) transfusion-independent prior to receiving rVA576 (Coversin) and remain transfusion-independent and ii) transfusion-dependent prior to receiving rVA576 (Coversin).
10. Proportion of patients experiencing Major Adverse Vascular Events (MAVE) over the entire period of the study.
11. Time to first Major Adverse Vascular Event (MAVE) for each subject since joining the study.
12. Number of Major Adverse Vascular Events (MAVE) over the entire period of the study.

aHUS Secondary:

1. Proportion of subjects with Normal Platelet count [defined as Platelet count $\geq 150 \times 10^9/L$] at each 3-month time point since the start of the study and over the entire period of the study.
2. Proportion of subjects entering study with complete TMA response who continue to exhibit complete TMA response with preserved renal function, defined as hematologic normalization (platelet count $\geq 150 \times 10^9/L$ and LDH \leq ULN) and preservation of kidney function ($<25\%$ increase in SCr from baseline of previous study), during each 3-month time period since the start of this study.
3. Proportion of subjects with complete TMA response with improved renal function defined as normalization of haematological parameters (normalisation of platelet count and LDH \leq ULN) and $\geq 25\%$ decrease in SCr from baseline of previous study during each 3-month time period since the start of the study.
4. Proportion of subjects who exhibit haematological normalisation (platelet count $\geq 150 \times 10^9/L$ and LDH \leq ULN) during each 3-month time period since the start of this study.

5. Proportion of subjects with improvement in renal function defined as a decrease in SCr over three consecutive measurements from baseline of previous study without the need for dialysis even if not within the normal range.
6. Proportion of subjects who are TMA event-free during each 3-month time period since the start of the study.
7. Platelet mean count change at each 3-month time period since the start of the study.
8. Quality of Life measures from baseline at 3 monthly intervals up to the end of study in FACIT-F instrument and the EQ-5D-5L instrument.

Additional Endpoints:

- PK and PD parameters during treatment.

4. Trial population

The study population will consist of patients who have completed participation in clinical trials under other Akari protocols and who wish to continue to receive rVA576 (Coversin). Patients may be male or non-pregnant females using adequate methods of contraception if of childbearing potential. All patients will enter the trial on the same dose and dose frequency as they were receiving at the end of the previous trial.

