2.3 Study Data

All patients enrolled into the CONSERVE study will have transitioned from a parent clinical trial and all will have been previously treated with rVA576.

Parent trial data used to assess patient safety and eligibility for enrollment will be entered into the AK581 database. Where applicable, assessment data collected at the subject's parent trial end of study visit will be captured. Coversin dosing history, parent trial ECG and LDH results, and plasma (blood) transfusion/dialysis history will be available in the AK581 subject casebooks.

Where applicable and where possible, parent trial locked databases will be used and pooled with the AK581 database:

- Raw data from AK578 CONSENT
- Study Data Tabulation Model (SDTM) and/or Analysis Data Model (ADaM) datasets from AK579 COBALT
- SDTM and/or ADaM datasets from AK580 CAPSTONE

See section 3.1, for the definitions of baseline (study entry) and parent trial baseline.

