3.2.4 Transfusions and Complement inhibitor history

Patients will be classified in subgroups as follows:

- i) Patients who were transfusion-dependent when they started receiving rVA576 (Coversin),
- ii) Patients who were transfusion-independent when they started receiving rVA576 (Coversin),

and further groupings will be performed as follows:

- a) Patients who were complement inhibitor-naïve prior to treatment with rVA576 (Coversin),
- b) Patients who received treatment with another complement inhibitor before of the switching to rVA576 (Coversin).

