4.11.1 Blood Transfusions

The proportion of subjects who require PRBC transfusion during each 3-month period since the start of the study and over the entire period of the study will be summarised. This summary will also be produced by subgroup of patients based on their transfusions and complement inhibitor history as defined in section 3.2.4.

The number of RBC or platelet transfusions per patient during the study will be summarised using descriptive statistics. Patients with no recorded transfusions will be included with an imputed count of zero.

The time (days) to first transfusion for each patient will be summarized using Kaplan-Meier methodology. Kaplan-Meier estimates of the proportion of patients receiving at least one transfusion during the study will be displayed with 95% two-sided confidence limits. The median, 95% Confidence Interval of the median, 25th and 75th percentiles of the time to first transfusion will be produced.

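### The planned transfusion summaries are not split by transfusion status at roll-over, so they do not directly measure whether the parent-trial effect is maintained

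*Protocol*

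**What the plan says.** Protocol 3.1 gives as one purpose to "show that the effect observed in the previous clinical trial is maintained". All patients enter already treated with rVA576.

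- **Endpoint 3** (Protocol 3.2.1, PNH secondary) is the proportion needing PRBC transfusion in each 3-month period and overall. It is reported for "subjects who were transfusion-dependent when they started receiving rVA576 (Coversin", for "subjects who were transfusion-independent when they started receiving rVA576 (Coversin" and for all subjects. The further split, for example "patients who were complement inhibitor-naïve prior to treatment with rVA576 (Coversin", also looks back to before rVA576.
- **Endpoint 4** is "Time to first transfusion since joining the study", with no grouping in its definition.
- **SAP 3.2.4** defines the transfusion subgroups only by pre-drug status ("Patients who were transfusion-dependent when they started receiving rVA576 (Coversin" and its counterpart). SAP 4.11.1 applies them to endpoint 3.
- **SAP 4.11.1** says of endpoint 4: "The time (days) to first transfusion for each patient will be summarized using Kaplan-Meier methodology". In SAP Appendix 1, Table 14.2.1.2 (time to first transfusion) has no subgroup version, whereas the endpoint 3 table has one.
- **Protocol 9.1** allows optional separate reporting, again by pre-drug status.
- **SAP 2.3** states that "plasma (blood) transfusion/dialysis history will be available in the AK581 subject casebooks" and that parent databases will be pooled where possible.

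Neither document defines transfusion status at roll-over or uses it as a subgroup or an at-risk set.

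**The concern.** Whether an effect is maintained is a question about patients who had the effect when they rolled over. For transfusion, those are the patients who were transfusion-free on rVA576 at entry to CONSERVE. A first transfusion in such a patient is a possible loss of effect. A transfusion in a patient still being transfused at entry is a continuing need. The pre-drug dependent stratum, the all-subjects row and the endpoint 4 curve combine the two.

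The mixture is plausible. Inclusion criteria 2 and 3 ask for clinician-judged benefit and sustained CH50 inhibition, not freedom from transfusion. Protocol 1.1 notes that patients with marrow aplasia are more likely to need transfusion because red-cell production is impaired.

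Nearby text does not isolate the group that matters. SAP 3.3.1 flags only patients who were independent before rVA576 and stayed so. Endpoints 9 and 8 are haemoglobin measures among transfusion-independent subjects. Table 14.2.1.4 summarises transfusion-independence, but the SAP gives no definition or look-back window for it. By contrast, aHUS secondary endpoint 2 takes as its denominator the subjects with complete TMA response at study entry.

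At stake is whether a reader of the report can tell persistent need from lost effect in the planned tables.

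**Working it through.** The documents give no expected transfusion rate, power or sample-size calculation for these endpoints, so there is no planned figure to reproduce. What follows is an illustration, and every hazard and share in it is an assumption.

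**Inputs (assumed, per quarter, constant within patient type)**
- Still transfused at roll-over: hazard H = 0.7, with 0.4 and 1.0 as a range.
- Transfusion-free at roll-over: hazard h = 0.03 if the effect is maintained, 0.15 if it is lost five-fold.
- s = share still transfused at roll-over.

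**Endpoint 3, quarterly proportion transfused**

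P = s(1 − e^−H) + (1 − s)(1 − e^−h), where 1 − e^−0.7 = 0.503, 1 − e^−0.03 = 0.030 and 1 − e^−0.15 = 0.139.

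| s | maintained | lost |
|---|---|---|
| 20% | 12% | 21% |
| 40% | 22% | 28% |
| 60% | 31% | 36% |

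Read across a row (fixed mix), the proportion rises when effect is lost. Read down a column, the level is driven by s: a result of 21% to 22% fits either maintained effect with s = 40% or lost effect with s = 20%.

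**Mix changing over time.** Protocol 5.4.3 allows withdrawal for lack of efficacy, Protocol 9.1 drops missing data from denominators, and Protocol 9.8 analyses efficacy time points in patients reaching them. Suppose s falls from 40% to 10% while the effect is lost:
- Start: 0.4 × 0.503 + 0.6 × 0.030 = 0.219.
- Later: 0.1 × 0.503 + 0.9 × 0.139 = 0.176.

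The proportion falls from 22% to 18% despite the five-fold loss. At H = 0.7 the loss is fully hidden once s drops below (0.219 − 0.139)/(0.503 − 0.139) = 22%. Over the range, the same change in s gives 15% to 16% at H = 0.4 (nearly flat) and 27% to 19% at H = 1.0.

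**Endpoint 4, transfusion-free at 12 months (4 quarters)**

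S = m e^−4H + (1 − m) e^−4h, with m = 0.5 not free at entry.
- Maintained: 0.5 × 0.061 + 0.5 × 0.887 = 0.474.
- Lost: 0.5 × 0.061 + 0.5 × 0.549 = 0.305.
- Free-at-entry group alone: e^−0.12 = 0.887 and e^−0.6 = 0.549.

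So the pooled figures are 47% and 30%, against 89% and 55%. The pooled drop is (1 − m) times the drop in the free-at-entry group, whatever H is: here 17 points against 34. With H = 0.4 the pooled figures are 54% and 38%; with H = 1.0 they are 45% and 28%.

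**The case against.** The strongest reply is that CONSERVE is one single-arm cohort, so what matters is the trend, and endpoint 3 is repeated every quarter. With a fixed mix, patients with constant need add a roughly constant amount and a loss of effect shows as a rise (22% to 28% at s = 40%). This stands. A reader might infer that the planned outputs would rank a maintained and a lost effect in the wrong order. They do so only if the case mix changes along with the effect. What survives is that the mix can change during follow-up through withdrawal, and that the level is not interpretable without it.

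Other points on that side:

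- SAP 3.1 refers some measures to the pre-drug state, and pre-drug transfusion status is the categorical equivalent. This is a consistent choice, so transfusion does not lack a reference. It answers change since before the drug, not maintenance since roll-over.
- A reader might call patients still transfused at roll-over non-responders. The documents do not support that: entry requires clinical benefit and CH50 inhibition, and marrow failure can require transfusion despite complement control.
- A reader might conclude that the data cannot separate the two groups. Only the planned summaries fail to. Parent history is to be in the casebooks and transfusions are listed.
- The stratum independent before rVA576 is largely unaffected, since any transfusion there is a new need.
- A pooled curve that flattens could be misread as improving control, but the SAP plans no hazard estimate, so that misreading is conjecture.

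**Conclusion.** The point holds as a limitation of the planned summaries. The pre-drug dependent stratum, the all-subjects row of endpoint 3 and the endpoint 4 curve mix continuing need with possible loss of effect, and no planned output separates them. Under the assumed hazards the pooled 12-month contrast is half that in the free-at-entry group when half of patients are not free at entry, and selective withdrawal can turn a five-fold loss into a flat or falling quarterly proportion. The sizes rest on assumed hazards and shares; the dilution by (1 − m) does not depend on the hazard in still-transfused patients.

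It would go too far to say that the trial cannot answer its question, or that its main efficacy outcome is compromised. The primary endpoint is safety, transfusion supplies two of twelve unranked PNH secondary endpoints, all analysis is descriptive, and LDH, haemoglobin, haemolytic events and quality of life also bear on maintained effect. This is a worthwhile, inexpensive improvement.

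**What to change.** - **SAP 3.2.4:** add transfusion status at CONSERVE entry, no PRBC transfusion versus at least one, over a pre-specified look-back on rVA576 in the parent trial (for example the last 3 months; the length is the sponsor's choice). Derive it from the history described in SAP 2.3, with a stated category for unknown status.
- **SAP 4.11.1:** report endpoint 3 by quarter and the endpoint 4 Kaplan-Meier summary by this status. Name the transfusion-free-at-entry group as the display for maintained effect.
- **SAP Appendix 1:** add a by-subgroup version of Table 14.2.1.2. Keep the pooled and pre-drug outputs.

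The cost is SAP wording, one derived variable and some table pages. The derivation may take effort: Protocol 5.7.1 has parent data transferred as PDF, SAP 2.3 pools databases only where possible, and there may be a lag before entry, so status may be unknown for some patients.

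Groups will also be small. If 25 of 50 patients are free at entry, the approximate 95% interval without censoring is 1.96 × √(0.887 × 0.113/25), or ±12 points, around 89%, and ±20 points around 55%. The pooled 47% in 50 patients would have ±14. Fixing the look-back in advance avoids choosing it after seeing the results.
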